- Post focus group questionnaire: 10 minutes

For **two (2)** Focus Groups: 4h40min

- Reading and explanation of the FIC: 20 minutes
- Balance tests: 20 minutes
- Equipment testing: 80
- Discussions: 140 minutes
- End questionnaire: 20 minutes

HUMAN, ANIMAL OR LIVING MATERIAL VOLUNTEER PARTICIPATION (number, characteristics (e.g. age, species), inclusion and/or exclusion criteria, recruitment method if applicable)

RV 50+ part

The recruitment pool will be formed from all seniors (non-members or members of FQLI, FADOQ, as well as residents of Le Groupe Maurice) who have responded to our recruitment ads in traditional and social media.

As far as the quantitative aspect is concerned, the questionnaire precedes the focus group. The recruitment pool is therefore the same as that of the focus groups.

On the qualitative side, we'll be recruiting around fifty (50) people aged 50 and over, with a proportional number in each age group: 50-54, 55-59, 60-64, 65-74, 75 and over. We'll set up focus groups around the virtual reality game trials, made up of 4 to 8 people.

Inclusion criteria

RV part

- Be aged 50 or over
- Being autonomous

Exclusion criteria

The following criteria apply to both the RV 50+ section and the intergenerational exchange section. The children's criterion applies only to the intergenerational exchange section.

- The experimental nature of the research requires participants to be fully physically fit. Consequently, people with functional limitations cannot participate in the study
- Group interviews require the sharing of experience, which presupposes the participation of people capable of communicating their opinions and reflecting collectively on their experiences. Thus, people with cognitive impairments are excluded from the research
- In view of the technology used for the research, people at risk of epilepsy cannot take part in this project
- Also, people with pacemakers are not eligible to participate in this research

SCIENTIFIC JUSTIFICATION FOR USING LIVE VOLUNTEERS

The participation of human volunteers representative of the clientele is essential in the phase of identifying needs and expectations in terms of activities and intervention methods according to age. This will enable us to develop physical and cognitive activity programs adapted to age and personal abilities in the next phase.

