The participation of teenagers (minors aged between 13 and 17) and adults is essential in the phase dealing with intergenerational bonding, exchange and sharing. This will then enable us to understand if and how immersive technology can support and foster the relationship between different generations, and thus influence the inclusion and active participation of all.

RECRUITMENT

RV 50+ part

In order to be representative of Quebec's 50+ population, posters will be displayed among Groupe Maurice residents, members of FQLI (Fédération québécoise du loisir en institution) and FADOQ (Fédération de l'Âge d'Or du Québec), in traditional media and on social media. In addition, will be posted on paper and electronically to target audiences and in cultural, community, sports and leisure venues, as well as in grocery stores where appropriate. Where necessary, members of the research team will visit the various locations to make the information more accessible. In addition, the TOPMED team may contact people who have previously expressed an interest in participating in a research project.

Potential participants can express their interest by calling or writing to TOPMED. A member of the project team will contact them to answer questions, ensure eligibility, forward documentation and/or arrange a telephone appointment at a later date if required.

The research team will then send an e-mail containing a link to the information and consent form and a physical activity questionnaire. Participants will be given two (2) weeks to review the documents and ask any questions they may have. Potential participants may contact the research team at any time if they have any questions or require assistance. A member of the research team will then be responsible for verifying the completion of the forms and the answers to the questionnaire.

The preliminary questionnaire for group interviews and a link to a booking calendar for group interviews will then be sent by e-mail.

A question about participating in future projects will be included in the pre-interview questionnaire. The participant is free to accept or decline.

During group interview meetings, the information and consent form will be reminded and re-explained. The physical activity aptitude questionnaire will be completed again and signed by the participant. The activity will then begin.

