- There are also risks associated with the use of immersive technologies. More specifically, discomfort linked to the graphics and the conflicting, multi-sensory aspect of immersion sessions could arise when using immersive technologies. This discomfort could take the form of cyberkinetosis akin to motion sickness, affecting participants to varying degrees: visual fatigue and headaches, temporary loss of visuo-spatial cues and dizziness, or nausea and even vagal discomfort. Although these symptoms are generally not serious, they should of course be spotted, and short sessions will be held to prevent them. In addition, the experimenter will be on hand at all times to ensure the participant's well-being. To this end, the members of the research team present will regularly ask questions about the sensations felt by the participant when trying out the activities. At the end of the focus groups, participants will be able to rest in a suitable space until any symptoms have disappeared. A member of the research team will remain with the participant for as long as necessary.
- Participants with pacemakers or at risk of epilepsy could experience more serious events and should therefore be withdrawn from the workshops.

Known or foreseeable risk(s)	Frequency and severity	Proposed mitigation measures	Warnings

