Feeling of discomfort	Proven risk	See measurements at the beginning of the table	
Nausea	Proven risk	-Ask participants to eat lightly before the test session to prevent the onset of symptoms.	
Saliva increase	Proven risk	See measurements at the beginning of the table	
Disorientation	Proven risk	See measurements at the beginning of the table	
Tachycardia	Proven risk	See measurements at the beginning of the table	Wearing a pacemaker or cardiac pacemaker is an exclusion criterion.
Loss of consciousness	Proven risk	See measurements at the beginning of the table	
Topic 2. Sensorimotor consequences (impaired manual dexterity, ability to orientate the body)	The risks presented under this theme are present and recognized in the literature.		
Contraction of eyes or muscles	Proven risk	See measurements at the beginning of the table	
Hand-eye coordination disorder	Proven risk	See measurements at the beginning of the table	
Involuntary movements	Proven risk	Prevention: Warm-up and stretching time before and after the trial	

Balance disorders	Proven risk	Suggested sitting, hydration	
Theme 3. Disruption of circadian rhythms (sleep onset, sleep time)	The risks presented under this theme are present and recognized in the literature.		-People considered sensitive: aphakics (lack of crystalline lens) and pseudophakics (artificial lens); people suffering from eye pathologies or abnormalities; people suffering from sleep disorders; people suffering from photosensitive epilepsy.
Sleepiness	Proven risk	See measurements at the beginning of the table	
Sleep time	Proven risk	See measurements at the beginning of the table	For people sensitive to blue light, avoid screens two hours before going to bed.
Topic 4. Epilepsy			
Epileptic seizures	Proven risk	-Pre-diagnosed epileptic risk is an exclusion criterion.	Taking neuroleptics favors the onset of epileptic episodes. This constitutes a contraindication to participation in the study.

Adapted from ANSES. (2021). Effets sanitaires potentiels liés à l'exposition aux technologies de réalité virtuelle et/ou augmentée. Collective expertise report

Mitigation measures :

- Monitoring symptoms of cyberkinetosis
- If they wish, they can end their participation in the group interview at any time.
- Snacks distributed to all participants

ADVANTAGES AND BENEFITS (personal benefit of their participation in the project, benefit to the project of their participation)

RV 50+ part

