Results will be coded. Participants will not be identified by name in the results, but will be identified by number. Any scientific publication resulting from this research project will present data in aggregate form, so that individual participants' results will never be communicated. Should the research team use extracts from verbatims, the participants' names will be replaced by a number.

DATA ACCESS

All research data will be accessible to the project team. Project sponsors will not have access to research data. Participants will not have access to research data. The Research Ethics Committee, Veritas IRB, will have access to research data for verification in the event of a complaint. Where appropriate, data will be made available to them for viewing only via videoconferencing.

CONTINUOUS EXAMINATION

Should any inconvenience arise following group interviews and the testing of immersive technologies, participants will be promptly notified.

DISSEMINATING RESULTS

No disclosure to patients will be made following the focus groups and questionnaires.

Results will not be published.

COMPENSATION

No remuneration is provided for participants.

DISASSEMBLY

Part VR 50+

There is no financial compensation for taking part in the preliminary questionnaire.

Financial compensation of \$25 is provided for participation in each meeting (\$50 in all). If necessary, a parking sticker may be provided for the duration of the participant's attendance at group interviews.

RESPONSIBILITIES

The legal rights of each participant will be maintained.

SEQUENCE

RV 50+ part

Process and data collection

Display

Postings in Groupe Maurice residences, among members of the FQLI (Fédération québécoise des loisirs en institution) and the FADOQ (Fédération de l'Âge d'Or du Québec) via traditional and social media, as well as in cultural, community, sports, leisure and food centers.

Related documents :

V4_Affiche_407_2023

407_Affich-Recrut

Admission

Validation by e-mail or telephone.

Interested parties can register their interest by e-mail or telephone call to TOPMED at the coordinates indicated in the recruitment notice.

Verification of eligibility criteria (age, ability to answer a questionnaire and give an opinion) and exclusion criteria (pacemaker wearer, epileptic risk) by a member of the research team.

Related document:

407_LabInt_Courriel

Validation for participation in FG

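### Neuroleptic use is a contraindication in the risk table but is missing from the exclusion criteria, the withdrawal statement and the admission check

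*Protocol*

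**What the plan says.** The risk table in the Protocol's section on risks and mitigation measures states three bars to taking part:

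- Pacemaker (tachycardia row, Topic 1): "Wearing a pacemaker or cardiac pacemaker is an exclusion criterion".
- Epileptic risk (Topic 4, mitigation column): "Pre-diagnosed epileptic risk is an exclusion criterion".
- Neuroleptics (Topic 4, same row, warnings column): "Taking neuroleptics favors the onset of epileptic episodes. This constitutes a contraindication to participation in the study".

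Three other places say who is kept out:

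- **Exclusion criteria** (volunteer participation section): four items, namely functional limitations, cognitive impairments, epilepsy risk and pacemakers. The last two read "In view of the technology used for the research, people at risk of epilepsy cannot take part in this project" and "people with pacemakers are not eligible to participate in this research".
- **Withdrawal statement** (risks section, just before the table): "Participants with pacemakers or at risk of epilepsy could experience more serious events and should therefore be withdrawn from the workshops".
- **Admission check** (Sequence, Admission): besides age and the ability to respond, the team verifies the "exclusion criteria (pacemaker wearer, epileptic risk) by a member of the research team".

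Neuroleptics are named once in the protocol, in the Topic 4 row.

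**The concern.** A contraindication protects participants only if someone is told to look for it before exposure. Here it stands in the warnings column of a risk table, while the criteria that staff verify leave it out. The table's general measures (asking about symptoms, limiting exposure, pausing or stopping, first aid) are mostly applied once the person is already in the session, so they do not replace screening.

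The protocol itself links the drug class to seizures, and the headset games are played both seated and standing. As the text stands, whether a contraindicated person is stopped before the trial depends on forms outside the protocol or on how a staff member happens to understand epileptic risk.

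**Working it through.** The protocol gives no figure to reproduce. The check is a comparison of texts.

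**Step 1. Trace each bar in the risk table to the three operative places.**

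| Bar in the risk table | Exclusion criteria | Withdrawal statement | Admission check | Total |
|---|---|---|---|---|
| Pacemaker | named | named | named | 1 + 1 + 1 = 3 of 3 |
| Epileptic risk | named | named | named | 1 + 1 + 1 = 3 of 3 |
| Neuroleptic use | absent | absent | absent | 0 + 0 + 0 = 0 of 3 |

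The epilepsy entries count as carried over although none of the three places repeats the table's restriction to a prior diagnosis.

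**Step 2. Ask whether the epilepsy item already covers neuroleptic users.** The Topic 4 row treats the two separately. Its mitigation cell limits the exclusion to a risk diagnosed beforehand, and its warnings cell adds neuroleptics as a distinct contraindication. Someone taking a neuroleptic with no seizure history has no diagnosed epileptic risk and could honestly answer no when asked about it. None of the three operative places tells staff to treat the drug as a marker of risk.

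**Step 3. Look for another step that would catch it.**

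- The preliminary questionnaire has a health section (measurement instruments section).
- A physical activity aptitude questionnaire is sent with the consent form, and a team member is responsible for "verifying the completion of the forms and the answers to the questionnaire" (Recruitment). Under Sequence it goes out once the eligibility and exclusion criteria have been checked. It is completed again and signed at the meeting (Recruitment).
- A screening e-mail is listed as a related document under Admission.

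The items in these documents are not shown. Any of them may ask about medication, but the protocol describes no medication question and ties no neuroleptic rule to any answer.

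**Result.** On the protocol's text alone, a neuroleptic user without a diagnosed epileptic risk meets no listed exclusion and fails no described check.

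**The case against.** The strongest reply is that the exclusion criteria and the admission check speak of epilepsy risk in general, without requiring a diagnosis. Since the table says that neuroleptics favour seizures, a user is at raised risk on the protocol's own reasoning and so already excluded. That reading is possible. It is not dependable, because the table row separates the two and the wording of the epilepsy criterion changes from place to place.

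Second, the withdrawal statement and the admission check are abbreviated. Functional limitation is a formal exclusion, yet neither of them names it. Absence from those two places is therefore weaker evidence than absence from the exclusion criteria. This stands, and the omission from the exclusion criteria carries most of the weight.

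Third, the forms may catch the case, and the aptitude questionnaire is repeated just before the activity. The consent form, not shown here, may also pass on the warning. This too stands: whether a user would actually reach the headset cannot be determined from the protocol.

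Fourth, the table's label of a proven risk adds little. Nearly every symptom row has it, including pallor and sweating, so it does not mark seizures as especially likely. That is correct, and the point does not rest on it.

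None of this removes the mismatch between the table and the exclusion criteria.

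**Conclusion.** The concern holds. The protocol sets a seizure-related bar to participation and then leaves it out of every list that staff are told to apply: 0 of 3 places, against 3 of 3 for each of the table's other two bars. Since those two were carried over, the omission looks like an oversight.

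The conclusion concerns the screening as written. It assumes that staff apply the exclusion criteria and the admission check as worded, and it makes no claim about the content of the unseen forms. The number of people affected is not estimated, because the protocol gives no rate of neuroleptic use and no seizure risk. No analysis is affected. This is a participant-safety inconsistency that should be fixed.

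**What to change.** 1. Add current neuroleptic use to the exclusion criteria.
2. Add it to the admission check under Sequence, with a medication question in the existing e-mail or telephone contact, before a session is booked.
3. Name it in the withdrawal statement in the risks section.
4. Choose one wording for the epilepsy criterion, either any risk or diagnosed risk, and use it in the exclusion criteria, the risk table, the withdrawal statement and the admission check.

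The cost is a few words of protocol text and one extra question in a contact that already takes place. A few volunteers may be screened out of the roughly 50 sought, but these are people whom the risk table already says should not take part.
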